528 *tapered off will be handled on a case-by-case basis after discussion with Study*
529 *Director/co-Director. See MOP for details.*
- 530 13. Presence of a medical condition that would contraindicate use of acetazolamide or
531 furosemide or significantly increase surgical risk
- 532 14. Pregnancy or unwillingness for a subject of childbearing potential to use contraception
533 during the first 6 months of the study
- 534 *Women of childbearing potential must use an acceptable form of birth control during the*
535 *first 6 months of the study. Acceptable forms include oral contraceptives, transdermal*
536 *contraceptives, diaphragm, intrauterine devices, condoms with spermicide, documented*
537 *surgical sterilization of either the subject or their partner, or abstinence.*
- 538 15. Presence of a physical, mental, or social condition likely to affect follow-up (drug
539 addiction, terminal illness, no telephone, homeless)
- 540 16. Anticipation of a move from the site area within six months and unwillingness to return
541 for follow-up at a SIGHT study site
- 542 17. Allergy to pupil dilating drops or narrow angles precluding safe dilation
- 543 18. Presence of a condition that contraindicates general anesthesia
- 544 19. Participation in an investigational trial within 30 days of enrollment that involved
545 treatment with any systemic drug therapy or therapy that affects the eligible eye(s)

546 **2.3 Eye-Level Eligibility Criteria**

547 To be eligible, an individual must have at least one eye meeting the following inclusion criteria
548 and none of the exclusion criteria.

549 If both eyes meet eligibility criteria, then both will be included in the primary outcome analysis.

550 **2.3.1 Eye-Level Inclusion Criteria**

- 551 1. Visual field loss meeting the following criteria based on two full threshold 24-2 size V
552 tests reviewed by the VFRC:
- 553 • PMD from -6 dB to -27 dB
 - 554 • Reproducible visual loss present on automated perimetry including no more than 15%
555 false positives
- 556 2. Visual acuity better than 20/200 (39 or more letters correct)

557 **2.3.2 Eye-Level Exclusion Criteria**

- 558 1. Intraocular pressure currently >28 mm Hg or >30 mm Hg at any time in the past
- 559 2. Refractive error of more than -6.00 or more than +6.00 sphere or more than 3.00 cylinder
- 560 with the following exceptions:
- 561 • Eyes with more than 6.00 D of myopia but less than 8.00 D of myopia are eligible if:

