634 stimulus size III may be performed prior to two size V tests if a recent size III result is not
635 available. The size III test can be used as a guide as to whether the subject is likely to have at
636 least one eye meet eligibility criteria when size V testing is done.

637 • PMD using the size III stimulus should be approximately in range of -8.5 to -30 dB.

638 Two size V stimulus fields will be performed in each eye.

639 • The two size V stimulus visual field examinations will be transmitted to the Visual Field
640 Reading Center which will evaluate the visual field results: In order for an eye to qualify
641 for the trial, the average PMD with stimulus size V will have to be equal to or worse than
642 -6 dB and better than -27 dB.

643 • If the Visual Field Reading Center confirms that the subject is eligible for randomization,
644 it will document the average mean deviation of the two size V tests as well as which eyes
645 qualify as eligible eyes.

646 • If the Visual Field Reading Center finds performance issues on the perimetry results, the
647 examination will need to be repeated for the subject to be considered for the randomized
648 trial.

649 *Depending on the subject's condition (e.g., suspected visual deterioration, fatigue), perimetry*
650 *may be repeated later that day, or up to the 3-day deadline for randomization; the only exception*
651 *being if a perimetry result is unreliable and requires a repeat examination, the site will have an*
652 *additional two working days to complete the visual field examination. These additional sets of*
653 *perimetry examinations will be submitted to the Visual Field Reading Center for*
654 *confirmation/denial of eligibility.*

655 There will be times that perimetry results are not reliable and a repeat examination will be
656 necessary. This may occur not only at the screening/baseline visit but also at any visit. Whenever
657 two examinations are required (baseline, 6 months, treatment failure protocol) the following
658 outcomes are possible:

659 1. Two examinations performed and: (1) performance criteria are met and (2)
660 pathophysiologic appropriate visual field patterns match. The average of the mean
661 deviations is used for the outcome. Acceptable performance criteria are: the false positive
662 rate is less than 15%, the false negative rate is judged not to be excessive for the amount
663 of visual loss, and gaze tracking data confirms acceptable fixation. All data from eyes in

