815 utilized (see MOP more details). The surgery will make a window in the dural sheath of at least 4
816 mm in length under the operating microscope. The procedure will be considered successful if
817 CSF egress is noted at the time of fenestration. Post-operative visits will be performed according
818 to the surgeon's usual routine.

- 819 • If both eyes meet study entry criteria, ONSF will be performed on the eye with the worst
820 PMD first, ideally within three days of randomization. If the other eye still meets eye-
821 level eligibility criteria at two weeks after surgery on the first eye, ONSF will be
822 performed on the second eye. If the second eye improves at two weeks after surgery on
823 the first eye and no longer meets eligibility criteria, ONSF will not be performed on that
824 eye.
- 825 • If only one eye meets entry criteria as an eligible eye, ONSF will be performed on the
826 eligible eye ideally within three days of randomization.
 - 827 ♦ If the second eye is not eligible for the study because visual field MD is too good, but
828 the eye worsens (i.e. PMD -6 dB or worse with size V perimetry at any time during
829 study follow-up), ONSF will be performed on the non-eligible eye. Also, if the non-
830 eligible eye meets criteria for temporary treatment failure (see section 5.6.3 below), it
831 will be operated on even if the PMD is not worse than -6 dB.
 - 832 ♦ If the second eye is not eligible for the study because visual loss is too severe, ONSF
833 will be considered at two weeks after surgery on the eligible eye.

834 See section 4.6, Management of the Non-Eligible Eye, for exceptions.

835 Administration of intravenous and topical corticosteroids is permitted intra-operatively, but
836 systemic corticosteroids are not to be administered post-operatively (see MOP for details).
837 Medical therapy will be continued until the Site Investigator believes that the dosage should be
838 stopped or decreased because the subject has improved; he/she may contact the Study co-
839 Director to decide on how to proceed. See section 4.1.4, Tapering of Medical Therapy.

842 **4.3 CSF Shunting**

843 CSF shunt surgery will occur ideally within 3 days of randomization by a certified neurosurgeon.
844 See MOP for surgeon qualifications. Using a frameless image-guided stereotactic system, a
845 ventricular shunt catheter will be positioned in the lateral ventricle of the cerebral hemisphere not

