4.6 Management of the Non-Eligible Eye

895 In general, non-eligible eyes are treated the same as eligible eyes. The non-eligible eye will have
 896 the same evaluations as the eligible eye. The only difference between eligible and non-eligible
 897 eyes is only the eyes that qualify at baseline (i.e., eligible eyes) will be included in the primary
 898 outcome analysis.

899 If a non-eligible eye worsens, the protocol for worsening of an eligible eye will be used. In the
 900 case of medical therapy, the dosage protocols for acetazolamide and if needed furosemide will be
 901 used. If there is worsening of a non-eligible eye in the optic nerve sheath fenestration group, the
 902 procedure will be performed on the 2nd eye if PMD worsens to -6 dB or worse with size V
 903 perimetry at any time during study follow-up or if the non-eligible eye meets criteria for
 904 temporary treatment failure (see section 5.6.3 below). If there is worsening of a non-eligible eye
 905 in the CSF shunting arm, medical therapy will be given and an evaluation for shunt failure will
 906 be done. Non-eligible eyes can be used to classify the subject as a treatment failure.

907 If only one eye meets study entry criteria and the other eye has worse vision by PMD than the
 908 eligible eye (e.g. PMD worse than -27 dB, refractive error too great, previous damage to the eye
 909 due to trauma, inflammation or infection) treatment of the eligible eye will take precedence; so in
 910 the case of optic nerve sheath fenestration, the eligible eye will be done first. However, there
 911 may be situations where the non-eligible eye requires the first operation. For example, if fixation
 912 is threatened only in the non-eligible eye. If the Site Investigator has concerns about the non-

913 eligible eye and believes it should be operated first, a decision will be made with the Study co-
914 Director as to which eye is operated first.

915 **4.7 Treatment during the Treatment Failure Identification Phase**

916 After the 26 Week primary outcome visit, subjects will transition to the Treatment Failure
917 Identification Phase. Ongoing treatment will continue following the guidelines for the first six
918 months (26 weeks) as long as treatment failure criteria are not met at which time treatment will
919 be at the discretion of the Site Investigator. Investigators are urged to employ treatments from
920 another arm of the study before other treatments under these circumstances.

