- 921 **Chapter 5: Study Visits and Procedures**
- 922 **5.1 Randomized Trial**
- 923 **5.1.1 Study Visits and Phone Contacts**
- 924 During the randomized trial, follow-up visits for all three groups will occur at weeks 4, 8 16, and
925 26 (± 7 days) timed from the day of randomization.
- 926 Post-operative visits may also be performed by the surgeon according to the surgeon's usual
927 routine.
- 928 Additional office visits may occur as needed.
- 929 Phone contacts will occur at 12 and 20 weeks (± 7 days).
- 930 **5.1.2 Safety Visits**
- 931 Safety visits will occur in addition to study visits, with the timing dependent on the treatment
932 group. The medical therapy only group generally will have visits 7 days and 14 days (± 4 days)
933 following randomization whereas the surgery groups generally will have visits 7 days and 14
934 days (± 4 days) following each surgical procedure. Visit schedules can be modified at
935 investigator discretion based on the participant's course and the 14-day visit could be skipped if
936 there is substantial improvement in papilledema after 7 days. Additional visits can be scheduled
937 as indicated. Reoperations at any time also will have a similar safety visit schedule.
- 938 **5.1.3 Study Visit Procedures**
- 939 The following procedures will be performed for all subjects at each study visit, unless otherwise
940 specified:
- 941 • Medical/IIH history update
 - 942 • Adverse Events
 - 943 • Concomitant Medications
 - 944 • Vital signs, including weight; (waist circumference at 26 Week only)
 - 945 • Clinical Laboratories
 - 946 • Refraction
 - 947 • Visual Acuity
 - 948 • Ocular Examination
 - 949 • Metabolic Panel (16 and 26 Week only)
 - 950 • CBC (16 and 26 Week only)
 - 951 • Humphrey visual field testing with 24-2 full-threshold program using size V stimulus
 - 952 ➤ at 26 Week, two visual field examinations

953 ➤ At other study visits, one visual field examination will be done, but the VFRC may
954 request the visual field examination be repeated

- 955 • Fundus Photographs
- 956 • OCT* (optic nerve head and macula)
- 957 • Dispense/prescribe acetazolamide and, if needed, furosemide
- 958 • Drug Compliance/Accountability
- 959 • Dietary counseling
- 960 • QoL questionnaires (26 Week only) – at study site or online
- 961 • HIT-6 questionnaire (26 Week only) – at study site or online
- 962 • Lumbar puncture for CSF opening pressure measurement (26 Week; voluntary)

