1011 An unscheduled visit can be performed at any time at investigator discretion, including the
1012 circumstance where the subject reports that IIH symptoms have worsened or if any unexpected
1013 adverse events develop. Testing performed and management decisions will be dependent on the
1014 circumstances of the visit and the findings.

1015 **5.4 Extra Assessments for Subjects Who Appear to be Worsening**

1016 If a subject appears to be worsening, the subject will receive a combination of frequent contact
 1017 (phone, text, email) and unscheduled visits. The Site Investigator will determine at the end of
 1018 each visit whether the subject appears to be worsening clinically [guidelines being: 1) subject
 1019 report of progressive visual loss, 2) papilledema is worsening, 3) OCT measures are worsening,
 1020 4) ETDRS acuity worsens more than 4 letters, or 5) PMD worsens more than 2 dB]. If the Site
 1021 Investigator is unsure how to proceed, he/she will review the case with the Study co-Director.

1022 **5.5 Early Termination**

1023 For subjects who are withdrawing or being withdrawn from the study, a final visit should be
 1024 scheduled as soon as possible.

1025 Procedures to be performed during the visit are the same as those listed in section 5.1.3.

1026 **5.6 Surgical Malfunction**

1027 VPS and ONSF malfunction will be evaluated at every visit if symptoms and findings suggest it.
 1028 If the Site Investigator, based on all clinical findings, believes that there may be a surgical
 1029 procedure malfunction/failure, he/she will request an SMRC review. Similarly, if the Photo
 1030 Reading Center or Visual Field Reading Center identify lack of improvement or worsening, a
 1031 SMRC review can be triggered.

1032 **5.6.1 Criteria for SMRC Review**

1033 Any of the below can trigger an SMRC review:

- 1034 1. Either visual criteria for treatment failure are met (see section 5.7.1)
- 1035 2. Papilledema: failure of papilledema to improve from baseline or worsening of
 1036 papilledema following improvement
- 1037 3. Site investigator believes there is substantial worsening of the subject's condition even if
 1038 none of the other criteria are met

1039 **5.6.2 Surgical Malfunction Review by SMRC**

1040 When triggered, the SMRC will review all available clinically-related information and reading
 1041 center results to determine whether there is a non-disease associated cause (mechanical cause)

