 1042 for the lack of improvement or worsening. The site surgeon and investigator will participate in
 1043 the review process as needed. The SMRC may request that certain exams be repeated for further
 1044 evaluation. The evaluation for VPS may include a radionuclide shunt study. The evaluation for
 1045 ONSF may consider orbital MRI or echography. If the SMRC believes a surgical malfunction is
 1046 likely, the subject's surgical procedure will be evaluated to check the viability of the procedure.
 1047 If the SMRC decides there was a problem with the surgery or a surgical device malfunction, they
 1048 will discuss the case with the site investigator, the surgeon, and the Study co-Director (or
 1049 committee member) to determine whether re-operation is indicated.

1050 The subject's safety is priority so if a site investigator or the SMRC Chair is confident a surgical
1051 malfunction occurred and emergent re-operation is needed, re-operation may be performed prior
1052 to full SMRC review.

1053 **5.6.3 Temporary Treatment Failure**

1054 Temporary treatment failure is a situation that can occur in either of the surgical arms where the
1055 subject meets criteria for treatment failure (see section 5.7.1) and then has their surgical
1056 procedure revised or, in the case of ONSF, either revised or the other eye operated on. If the
1057 subject then recovers vision and no longer meets the criteria for treatment failure, they will
1058 continue the protocol treatment. If repeat surgery is not successful in improving vision out of the
1059 treatment failure criteria range, the case goes to the Adjudication Committee to determine if
1060 treatment failure has occurred.

1061 **5.7 Treatment Failure**

1062 Possible treatment failure will be evaluated at every visit if symptoms and findings suggest it. If
1063 the Site Investigator, based on all clinical findings, believes that there may be a treatment failure,
1064 the worsening will be confirmed with a repeat visual field examination (and ETDRS acuity
1065 testing if needed) on the same day or within four days of the original visual field. If the Visual
1066 Field Reading Center identifies lack of improvement or worsening, the site will be notified and
1067 repeat testing performed. If the worsening is confirmed (both visual field examinations having
1068 PMD that exceeds the cutoff value in 5.7.1 below), the case goes to the Adjudication Committee
1069 to determine if treatment failure has occurred.

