1070 **5.7.1 Treatment Failure Criteria**

1071 If either of the below criteria for worsening are met, the subject will be considered for treatment
1072 failure by the Adjudication Committee:

- 1073 1. Worsening of Full Threshold Size V 24-2 Perimetry.
- 1074 a. Average baseline MD is equal to or better than -4 dB and visual function worsens
1075 more than 2 dB MD from the baseline average.
- 1076 b. Average baseline MD is worse than -4 dB and equal to or better than -6 dB and
1077 visual function worsens more than 3 dB MD from baseline average.
- 1078 c. Average baseline MD is worse than -6 dB and visual function worsens more than
1079 4 dB MD from baseline average.
- 1080 2. Worsening of 2 or more lines of ETDRS visual acuity

1081 **5.7.2 Treatment Failure Review by Adjudication Committee**

1082 The Adjudication Committee will review possible treatment failures and determine if a treatment
1083 failure has occurred. The committee will be masked to treatment assignment and using all
1084 available clinically-related information, including fundus photo results, will decide whether the
1085 failure is most likely due to increased intracranial pressure or from another cause, such as
1086 perimetric artifact, poor subject effort, or the presence of another unrelated cause of visual loss.

1087 If the Adjudication Committee determines that a possible treatment failure is most likely due to
1088 IIH, the subject will be classified as having experienced a treatment failure. All cases that are
1089 sent to the Adjudication Committee will be reviewed first by the Study Director. If it is obvious
1090 that the patient meets criteria for treatment failure, they will be so designated. The case will
1091 subsequently be reviewed by the Adjudication Committee.

1092 When a subject meets the criteria for treatment failure, it is preferred that subsequent therapy
1093 come from one of the other two treatment arms but this decision will be deferred to the judgment
1094 of the Site Investigator. These subjects will continue to be followed at their set times for the full
1095 follow-up period (up to 3 years). The date of a confirmed treatment failure will be the date of the
1096 first visual field that triggered the Adjudication Committee review.

1097 If treatment failure is not confirmed, the subject will continue to follow his/her treatment group's
1098 protocol.

1099

[figure not shown]
1100

Figure 3. Algorithm for Review by Surgical Malfunction Review Committee

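### ONSF on a fellow eye that was too good for entry can follow from a single size V field, because no section makes the operation wait for a confirming field

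*Protocol*

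**What the plan says.** Protocol 4.2 covers a subject in the ONSF arm with one eligible eye and a fellow eye that was not eligible because its field was too good. Surgery on that fellow eye is mandatory if "the eye worsens (i.e. PMD -6 dB or worse with size V perimetry at any time during" follow-up. Section 4.6 states the same rule: the "procedure will be performed on the 2nd eye if PMD worsens to -6 dB or worse with size V" perimetry. Meeting the criteria for temporary treatment failure is a separate, alternative route to surgery in both sections.

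Other sections set how many fields are taken and when they must be confirmed:

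- Eye-level entry (2.3.1): "Visual field loss meeting the following criteria based on two full threshold 24-2 size V" tests, reviewed by the Visual Field Reading Center (VFRC).
- Treatment failure (5.7): "the worsening will be confirmed with a repeat visual field examination (and ETDRS acuity" testing if needed), the same day or within four days, with both fields beyond the cutoff.
- Two-field occasions (2.4.1.1): the rules apply whenever "two examinations are required (baseline, 6 months, treatment failure protocol) the following" outcomes are possible. The -6 dB fellow-eye rule is not on that list.
- Visits before Week 26 (5.1.3): "At other study visits, one visual field examination will be done, but the VFRC may" ask for a repeat.

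**The concern.** The rule applies throughout follow-up and the surgery is not optional. Read literally, one reliable field at -6 dB or worse is enough to send the eye to orbital surgery. A fellow eye whose true PMD is stable a little better than -6 dB will cross that line on some visits through retest variation alone, and repeated visits add up the chances.

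The operation cannot be undone. Protocol 1.3.2.2 reports worse vision after ONSF in 13% of patients in the pooled case series, and 9.8.1 lists surgery-associated visual loss and orbital infection among the events of particular concern. In 1.2.2 the protocol itself faults an earlier ONSF series for judging worsening on one field and says that confirmation was needed. That remark is about eyes with moderate to severe damage, so it supports the principle but gives no figure for a milder fellow eye.

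**Working it through.** **Is a confirming field required anywhere on this route?**

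- 4.2 and 4.6 state the threshold and the operation, and no second field. The exceptions that 4.2 refers to in 4.6 concern which eye is operated on first.
- 2.4.1.1 requires a repeat when a field is unreliable. A reliable first field needs none.
- 5.1.3 lets the VFRC ask for a repeat but does not oblige it to.
- 4.6 says in general terms that a worsening non-eligible eye follows the eligible-eye protocol, then sets the -6 dB rule for the ONSF arm separately.
- 5.7 calls for repeat testing when the VFRC identifies worsening. That step belongs to treatment failure and its cutoffs; 4.2 and 4.6 do not make surgery wait for it.

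So no section makes this operation conditional on a second field.

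**How often could noise alone meet the rule?** The plan gives no figure to reproduce. The following is an illustration.

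Inputs from the protocol: threshold -6 dB (4.2, 4.6); five one-field visits at Weeks 1, 2, 4, 8 and 16 (1.8.1). Assumed: normal, independent retest errors with SD 0.5, 0.8 or 1.2 dB, and a true PMD μ that does not change.

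For one field, p = Φ((-6 - μ)/SD).

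- One-field rule over five visits: 1 - (1 - p)^5.
- Confirmed rule (both fields at -6 dB or worse): 1 - (1 - p²)^5.

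Example, μ = -5 and SD = 0.8: p = Φ(-1.25) = 0.1056. One field: 1 - 0.8944^5 = 0.428. Confirmed: p² = 0.0112, so 1 - 0.9888^5 = 0.055.

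Chance of meeting the rule at least once (SD 0.5 / 0.8 / 1.2):

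| Fellow eye | One field | With confirming field |
|---|---|---|
| Stable at -4 dB | 0% / 3% / 22% | 0% / 0% / 1% |
| Stable at -5 dB | 11% / 43% / 68% | 0.3% / 5.5% / 19% |
| Stable at -5.5 dB | 58% / 79% / 87% | 12% / 31% / 46% |
| Stable at -5.9 dB | 93% / 95% / 96% | 62% / 68% / 71% |
| -5 dB, gains 1 dB by Week 8 | 2% / 17% / 43% | 0% / 1% / 7% |
| -5 dB, gains 2 dB by Week 8 | 1% / 9% / 28% | 0% / 0.5% / 4% |

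The last two rows use a linear gain to Week 8, then a flat course, with p computed at each visit and 1 - p (or 1 - p²) multiplied across visits. If the Week 2 visit is skipped, as 5.1.2 allows, the stable -5 dB row becomes 9% / 36% / 60% against 0.2% / 4% / 15%.

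**What does confirmation cost in detection?** The chance that a truly worse eye meets the rule at one visit falls from p to p²:

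| True PMD | One field | With confirming field |
|---|---|---|
| -7 dB | 98% / 89% / 80% | 95% / 80% / 64% |
| -8 dB | 100% / 99% / 95% | 100% / 99% / 91% |

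**The case against.** The strongest reply is that -6 dB is the trial's own entry limit. The rule asks whether the fellow eye has reached the severity at which the trial gives its assigned treatment, and an absolute threshold is coherent for that question. This stands. A reader might infer that the rule is wrong because it sets no minimum change: 5.4 lists "4) ETDRS acuity worsens more than 4 letters, or 5) PMD worsens more than 2 dB" as a sign of worsening, and 5.7.1 requires, for a baseline worse than -4 dB and no worse than -6 dB, that "visual function worsens more than 3 dB MD from baseline average". The documents do not support that reading. Section 5.4 prompts extra contact and visits, and 5.7.1 asks whether assigned therapy has failed. Those rules serve other purposes, and the absence of a minimum change here is a design choice.

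It can also be said that the rates rest on assumed SDs and on an eye that does not improve, while every subject receives medical therapy and the first eye has been operated on. That is fair: the improving rows are much lower. The model also leaves out clinical judgement, surgical scheduling and consent. The VFRC checks every examination (10.5.2), 5.4 offers co-Director review when the investigator is unsure, and 6.5 leaves perimetry detail to a manual that is not available here. These safeguards may well prevent some operations, but none of them, as far as the two documents show, obliges anyone to confirm a reliable reading.

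Finally, confirmation is not free. At a true -7 dB the one-visit detection loss at the two larger SDs (89% to 80%, 80% to 64%) is not slight, and delay matters in this disease. Later visits, the temporary treatment failure route and an emergency exemption offset it.

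**Conclusion.** The gap is in the text and does not depend on the illustration: surgery on a too-good fellow eye is mandatory at -6 dB or worse, and no section requires a reliable first field to be confirmed, whereas entry and treatment failure both rest on two fields. An unseen manual could add a check, but 4.2 and 4.6 do not cite it for this rule.

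The size depends on assumed SDs, independent errors and little improvement. The problem is confined to single-eligible-eye subjects in the ONSF arm whose fellow eye lies near -6 dB. Confirmation reduces false triggers substantially at -5 dB, but a stable -5.9 dB eye would still meet the rule in 62% to 71% of cases. If errors are shared between two fields taken close together, the gain is smaller than shown.

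Two further inferences are not supported. One is bias in the primary result: the fellow eye is outside the primary analysis, and nothing here demonstrates an effect on the estimate. The other is a count of unnecessary operations, for which the documents give neither the number of such eyes nor a retest SD. This is a low-cost improvement for patient safety, worth considering, with medium confidence.

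**What to change.** Add to 4.2, and to the matching sentence in 4.6: Before ONSF on a non-eligible eye under the -6 dB rule, a second size V field is obtained the same day or within four days, and both fields must be -6 dB or worse on VFRC review; emergent cases are exempt. Add this trigger to the list of two-field occasions in 2.4.1.1. The threshold and the temporary treatment failure route stay as they are.

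The cost is one extra non-invasive field per trigger, up to four days' delay, and the lower one-visit detection shown above. No additional subjects are needed.
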